8.2.3 Immediate Reporting of Adverse Events

8.2.3.1 Serious Adverse Events

A serious adverse event is any adverse event occurring at any dose or during any use of Merck's product that:

- Results in death;
- Is life threatening;
- Results in persistent or significant disability/incapacity;
- Results in or prolongs an existing inpatient hospitalization;
- Is a congenital anomaly/birth defect;
- Is a new cancer (that is not a condition of the study);
- Is associated with an overdose;
- Is another important medical event

Progression of the cancer under study is not considered an adverse event unless it results in hospitalization or death.

Any serious adverse event, or follow up to a serious adverse event, including death due to any cause other than progression of the cancer under study that occurs to any subject from the time the consent is signed through 90 days following cessation of treatment, or the initiation of new anti-cancer therapy, whichever is earlier, whether or not related to MK-3475, must be reported within 2 working days of learning to the Principal Investigator and to Merck Global Safety.

Additionally, any serious adverse event, considered by an investigator who is a qualified physician to be related to MK-3475 that is brought to the attention of the investigator at any time outside of the time period specified in the previous paragraph also must be reported immediately to the Principal Investigator and to Merck.

SAE reports and any other relevant safety information are to be forwarded to the study coordinator and the Merck Global Safety [contact]

All subjects with serious adverse events must be followed up for outcome.

8.2.4 Evaluating Adverse Events

An investigator who is a qualified physician will evaluate all adverse events according to the NCI Common Terminology for Adverse Events (CTCAE), version 4.0. Any adverse event which changes CTCAE grade over the course of a

given episode will have each change of grade recorded on the adverse event case report forms/worksheets.

All adverse events regardless of CTCAE grade must also be evaluated for seriousness.

9.0 CORRELATIVE STUDIES

Response rates to PD-1 and PD-L1 targeted agents indicate that a subset of patients derive greater benefit from this treatment strategy, whereas some patients have no benefit. To complement this study and increase its scientific yield, we are proposing several scientific correlates in an attempt to identify potentially predictive biomarkers for MK-3475. While these are unlikely to be definitive, based on the relatively small numbers of patients involved, the data collected will help guide the development of potential biomarkers in future studies as well as identify patients most likely to benefit or not benefit from MK-3475. Some of these studies will be limited to patients randomized to the treatment arm.

Preliminary data suggest that tumor PD-L1 expression may be a predictive marker for MK-3475 (18). In an effort to characterize PD-L1 expression in SCLC, we will collect archived tumor specimens from all participants for PD-L1 expression analyses. PD-L1 expression will be assessed by QualTek Clinical Laboratories, Pennsylvania. Tissue for PD-L1 testing should be sent to QualTek Clinical Laboratories, [name]. Tumor tissues by participating sites will be sent to [name], Director of the Biobanking and Correlative Sciences Core at Karmanos Cancer Institute. Address for shipping is the same as shipping blood for CTC assessment as mentioned in section 9.1.

Tumor content in diagnostic biopsies is likely to be limited in SCLC patients. In addition, serial biopsies are challenging in patients with SCLC. Also after completion of chemotherapy, biopsy of residual tumor may be challenging. Circulating tumor cells (CTCs) hold great promise as a readily available source material that can offer real-time insight into a tumor's genomic architecture as well as tumor burden. CTCs can be detected in small cell lung cancer patients and appear to have prognostic importance (20, 21). [name], Director of the Biobanking and Correlative Sciences Core will supervise quantitation of CTCs in patients enrolled on this study. Peripheral blood (8 mL) will be collected into a Cell Search CTC collection tube. Tumor cells are then subject to negative immunomagnetic selection with anti-CD45 antibodies and positive immunomagnetic selection with EpCAM antibodies and fluorescently labeled for quantitation. These fluorescently labeled cells can be stained for PD-L1 for correlation with tumor progression assessment. Alternatively, the immunomagnetic platform allows isolation of EpCAM selected cells from the peripheral blood from which mRNA can be reverse-transcribed for RT-PCR. Using beta-actin as an internal control, mRNA expression levels of target genes can be ascertained. As a correlate to this trial, we will collect blood prior to therapy on the first day of the first cycle, on the first day of second cycle, and first day of the third cycle. After processing, samples will be shipped to the [name] laboratory (see shipping address and conditions below). Both

CTC counts and assessment of PD-L1 protein and mRNA expression in isolated CTCs will be done.

9.1 Shipping of CTC samples to Karmanos Cancer Institute

Blood (min. 7.5 ml) for CTC counting will be collected in a Cell Save purple and yellow marbled topped tube. Blood for CTC isolation needs to be collected in an EDTA tube. Both specimens should remain at room temperature.

Blood for CTC samples should be shipped within 24 hr. to the address below at ambient temperatures. The tubes are glass and special care needs to be taken to ensure the tubes do not break. Bubble wrap pouches with extra cushioning works best.

Ship to:
Biobanking and Correlative Sciences Core
Attn: [name]
Wayne State University/Karmanos Cancer Institute
[name]
[name]
[name]
PH: [contact]

10.0 DEFINITIONS OF END POINTS

All patients who are registered and have received at least one dose of the study drug will be eligible to be considered for all the following end points-

10.1 Primary Endpoint- RECIST 1.1 defined Progression Free Survival (PFS)- PFS is defined as the duration of time from registration to time of progression. Patients who die without reported prior progression will be considered to have progressed on the day of their death. Patients who did not progress will be censored at the day of last tumor assessment.

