2.0 TRIAL DESIGN

2.1 Trial Diagram

The primary end point of the study is to assess Progression Free Survival (PFS) by RECIST 1.1. However it is well recognized that patients on immune check point inhibitors may experience pseudo-progression or can have delayed response. Therefore patients who do not have development of significant signs or symptoms of progression or significant decline in performance status or the patient/the treating physician feel the need to start next treatment, will require evidence of progression on 2 scans more than 4 weeks apart. Both RECIST defined PFS and **this modified PFS** will be reported for all patients enrolled on the trial.

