6.6 Subject Replacement Strategy

Patients will only be replaced if the patient withdraws consent before the first dose of therapy.

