8.0 TRIAL PROCEDURES

8.1.1 Registration Procedures

Eligible patients will be entered on the study centrally at the clinical trials office of the Karmanos Cancer Center/Wayne State University, by, the Study Coordinator (or a designated study coordinator). All sites should call the Study Coordinator) after initiating screening.

An eligibility check list will be generated by the Study team at Karmanos Cancer Institute. This eligibility check list has to be completed by each site and signed by the responsible investigator. Once this is received by Study Coordinator and confirmed by him/her, the patient will be registered. A registration confirmation will be sent to the site (sites other than Karmanos Cancer Institute).

Once registration has occurred patient has to be treated within 5 days. If patient does not start therapy within 5 days of registration, the reasons for delay should be communicated to the Principal Investigator. He will then decide if the patient can continue on study therapy.

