11.0 STATISTICAL ANALYSIS PLAN

11.1 Study Design and Primary Endpoint

This is a single arm Phase II study to evaluate the efficacy of consolidation MK-3475 in extensive stage SCLC patients following completion of 4 cycles of chemotherapy with cisplatin or carboplatin and etoposide and whose disease has either responded or stabilized following chemotherapy. We propose a single arm study since the standard initial therapy for SCLC is well established for the last 20 years and the median PFS following such induction therapy is well defined, making a randomized study with control arm less necessary.

The primary endpoint is PFS with RECIST criteria defined as duration of time from registration to time of progression. Patients register after the induction chemotherapy is completed and have achieved stable or responding disease. Patients who die without reported prior progression will be considered to have progressed on the day of their death. Patients who did not progress will be censored at the day of last tumor assessment. PFS has been the primary endpoint in most maintenance trials conducted in SCLC patients to date.

11.2 Sample Size and Accrual Rate:

The median PFS in SCLC patients who have stable or responding disease following initial chemotherapy is approximately 2 months. We expect that the experimental treatment will improve the median PFS 50% to 3 months. Assume an exponential and one-sided alpha 0.05, 40 patients accrued in 18 months with minimum follow-up time 6 months will achieve 80% power to test the null hypothesis that median PFS is 2 months versus the alternative of 3 months.[PASS14.0.7] (29). In this protocol, we assume about 10% of patients will be ineligible. Thus, a total of 45 will be enrolled to study. To assess the efficacy, we will follow each patient to at least 6 months or progression.

It is estimated that approximately 28 patients per year should be accrued once the study is open at all sites (4-5 sites). Thus, the accrual duration will be about 18 months and the study duration is 24 months including the 6 months follow-up. All patients will be followed for PFS and OS to evaluate the clinical benefit of MK-3475.

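### PFS is timed from registration but analysed only in patients later dosed, so recognised pre-dose failures drop out; the bias within the trial favours the drug but is probably small

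*Combined protocol and SAP*

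**What the plan says.** Section 10.0 sets one analysis population for every endpoint: "All patients who are registered and have received at least one dose of the study drug will be eligible to be considered for all the" endpoints that follow. Section 10.1 then sets the clock: "PFS is defined as the duration of time from registration to time of progression". Section 11.1 repeats that origin: "The primary endpoint is PFS with RECIST criteria defined as duration of time from registration to time of progression". Both sections count deaths: "Patients who die without reported prior progression will be considered to have progressed on the day of their death". Under 10.0, that rule reaches only patients who were dosed.

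Section 6.0 calls for first dose within 5 days of registration. Section 8.1.1 leaves room beyond that: "If patient does not start therapy within 5 days of registration, the reasons for delay should be communicated to the Principal Investigator", after which the Principal Investigator decides whether the patient stays on study. No upper limit is given. On replacement, 6.6 says: "Patients will only be replaced if the patient withdraws consent before the first dose of therapy". A pre-dose death or deterioration is therefore not replaced.

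Two further places bear on this. Section 2.1 says that both PFS versions "will be reported for all patients enrolled on the trial", and 3.2 uses similar wording for modified PFS. OS runs from registration in 10.2 but from start of treatment in 11.3.

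**The concern.** Entry to the analysis depends on something that happens after the clock has started. A patient who dies between registration and first dose leaves the analysis set, although the endpoint definition would otherwise make that death an event. A patient whose decline is noticed in that interval, and who is never dosed, leaves in the same way. Everyone who remains carries the waiting time as PFS.

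Both effects lengthen PFS. The trial has no control arm that would share them, and the result is judged against a fixed median of 2 months in a disease that the protocol describes as relapsing quickly. Section 8.1.1 adds a further route: whether a late starter enters the primary analysis can rest on a decision taken once the reason for delay is known. No sensitivity analysis is planned with another origin or population.

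**Working it through.** **Inputs.** From 11.2: exponential PFS, null median 2 months, alternative 3 months, one-sided alpha 0.05, 80% power, 40 patients, 18 months' accrual, 6 months' minimum follow-up, 45 enrolled. From 6.0: a gap of 0 to 5 days. From 4.1: median survival of about 10 months. Assumptions: the test, the distribution of gaps and the share of pre-dose failures recognised, none of which the plan gives.

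**1. The plan's own figure.** Events = (1.645 + 0.842)² / (ln 1.5)² = 37.6. With λ₁ = ln 2/3 per month, the event probability is 1 − [exp(−6λ₁) − exp(−24λ₁)]/(18λ₁) = 0.941. N = 37.6/0.941 = 39.97, so 40, with 80.0% power. Then 40/0.9 = 44.4, so 45. The stated sample size reproduces and is not in question.

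**2. Most that could be lost inside the window.** With λ₀ = ln 2/2 per month and 5 days = 5/30.44 = 0.164 month, the null probability of failure before dosing is 1 − exp(−0.3466 × 0.164) = 5.5%, or 2.5 of 45. For a 2.5-day gap it is 2.8%, or 1.3 of 45. If every such failure were removed, the apparent null median would be 2.16 months at 5 days and 2.08 at 2.5 days. That is 16% and 8% of the 1-month gain sought.

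**3. How much would be recognised.** No scan is scheduled between registration and first dose; restaging comes after every 2 cycles (7.1, 8.1.4.2). A silent progressor is dosed, stays in the set and counts as an early failure. Only deaths and clinically evident decline can drop out. For deaths alone, at a 10-month median, 1 − exp(−(ln 2/10) × 0.164) = 1.1% over 5 days (0.5 of 45). At an assumed 6-month median it is 1.9% (0.8 of 45). Those are about 20% and 34% of the 5.5% in step 2, so 10% to 50% recognised is a reasonable range.

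**4. False-positive rate.** Simulated trials of 40 dosed patients under the null use the exponential event rate as test statistic, with its critical value calibrated to 5% when there is no gap.

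| Gap to first dose | Pre-dose failures removed | False-positive rate |
|---|---|---|
| Uniform 0–5 days | 10%, 20%, 30%, 50% | 5.2%, 5.3%, 5.5%, 5.8% |
| Uniform 0–5 days | all | 6.8% |
| Everyone on day 5 | 10%, 20%, 30%, 50% | 5.3%, 5.6%, 6.0%, 6.7% |
| Everyone on day 5 | all | about 9% |

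In the first row about 0.1 to 0.6 of 45 patients are lost.

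**5. Dependence on the test.** An uncalibrated Wald test on the log hazard starts at 3.9% with no gap. With all pre-dose failures removed it gives about 5.4% for the uniform gap and 7.3% when everyone is dosed on day 5. For assumed delays of 7 and 10 days, beyond the normal window, it gives 9.3% and 12.9%.

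**The case against.** A treated-patient set is common in single-arm phase II trials, and the window is short. Patients must be non-progressing, ECOG 0 or 1, with recent adequate organ function, so few should die or visibly fail within 5 days. Same-day dosing removes the effect altogether. Section 11.3 plans Kaplan-Meier estimates with 95% intervals and names no test, so any false-positive rate is conditional on a test the reader supplies. The largest in-window shift, 0.16 month, is small beside a benchmark given only as approximately 2 months. All of this stands, and it limits the size of the problem. It does not remove the mismatch between origin and population.

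Some stronger readings are tempting, and the documents do not support them:

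- *The pre-dose interval is event-free by rule.* That is strict only for death. Nothing in 10.0 or 10.1 bars progression before dosing from counting in a patient who is later dosed, and unrecognised progression stays in the set.
- *Comparison with the 2-month null must favour the drug.* The direction is clear only within this trial. Section 4.1 describes the historical figure as following disease stabilisation, without clock start or analysis set. A similar gap there would offset part of the bias.
- *Sections 2.1 and 3.2 name the opposite population.* They refer to enrolled patients, and enrolled is never defined against registered or dosed. This is loose wording to be aligned.

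**Conclusion.** The mismatch is real and worth correcting. PFS runs from registration in a set defined by later dosing, so recognised pre-dose failures disappear without replacement and the waiting time is credited as PFS. Within this trial the bias favours the drug; its net size against the benchmark cannot be determined from the documents.

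The effect is probably small: a nominal 5% becomes about 5.2% to 5.8% with uniform gaps over 0 to 5 days and 10% to 50% of pre-dose failures recognised. The 6.8% figure needs every pre-dose failure removed. About 9% is the upper bound within the window and also needs everyone dosed on day 5, with at most 2.5 of 45 patients lost. A reader might take 9%, or the roughly 11.5% obtained by deleting the three earliest failures of 40, as the expected effect. The first is the extreme corner, and the second exceeds the expected maximum loss.

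These figures assume exponential PFS at the null median and a calibrated exponential test. They do not cover delays beyond 5 days, which 8.1.1 permits without limit. The bias cannot by itself turn 2 months into 3.

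**What to change.** Make time origin and population agree, in one of two ways:

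- **Dosed patients from first dose.** Keep the population in 10.0 and start PFS, modified PFS and OS at first dose. Edit 10.1, 10.2 and 11.1; 11.3 already times OS from start of treatment.
- **All registered eligible patients from registration.** Count death or progression before first dose as an event. Edit 10.0 and 11.1, and change the OS origin in 11.3 to registration so that it matches 10.2.

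Report the version not chosen as a sensitivity analysis, and have 2.1 and 3.2 name the same population as 10.0.

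The cost is a few sentences. Registration and first-dose dates should already be on record, and the sample size stays at 40 analysed and 45 enrolled. The downside is a PFS estimate that may be slightly less favourable.

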10.2 Secondary Endpoints-

Modified Progression Free Survival- Modified PFS requires that RECIST defined PFS is confirmed by a second scan at least 4 weeks apart. Following issues need to be considered

- a. New lesion/lesions are considered as progression in RECIST defined PFS. However for modified PFS the largest unidirectional measurement of new lesion/lesions will be added to the total tumor measurement. If this exceeds 20% on 2 consecutive scans then the patient will be considered to have tumor

progression according to modified PFS criteria. A new lesion or lesions alone will not qualify for this modified PFS definition.

- b. If patients who have RECIST defined progression are symptomatic or have decline in performance status or develop unacceptable laboratory abnormalities and the treating physician and/or the patient decide to discontinue therapy or change therapy then the second scan confirming progression is not required.

Overall Survival- Overall survival is defined as the time from registration to time of death. If the patient is lost to follow-up, survival will be censored on the last date the patient was known to be alive.

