3.2 Secondary Objective(s) & Hypothesis(es)

1. To assess modified PFS in all patients enrolled (**see section 10.2 for definition**).
2. To assess overall survival of patients enrolled on the trial.
3. To assess PD-L1 expression in archival tumor tissues and in circulating tumor cells (CTCs) and correlate the expression to RECIST defined PFS.

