4.2.3 Rationale for Efficacy Endpoints

We have selected progression free survival as defined by RECIST criteria as the primary endpoint. This was the primary endpoint in most maintenance trials conducted in SCLC patients to date. Consistently the median PFS in these maintenance trials following induction therapy in responding or stable disease patients is about 2 months in the control arm. Therefore it will be possible to assess if the results with maintenance MK-3475 are better than this historical data and thus encouraging enough to continue further evaluation of this drug in this setting.

It is well recognized that patients treated with immune therapy may have pseudo progression or can have delayed response. Therefore many trials of immune therapy assess not only PFS as defined by RECIST criteria but also a modified PFS. The modified criteria require progression on 2 sequential scans, at least 4 weeks apart for definition of progression. The patients will continue on study therapy until these criteria are met, unless there is a decline in patient's performance status or symptoms that is considered not acceptable by the patient or the treating physician, or the patient wants to discontinue therapy for any reason.

In this trial we will not only assess PFS by RECIST criteria but will also assess PFS by this modified criteria as well. In addition we will assess response to MK-3475 by RECIST and overall survival.

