6.5 Subject Discontinuation Criteria

Subjects may withdraw consent at any time for any reason or be dropped from the trial at the discretion of the investigator should any untoward effect occur. In addition, a subject may be withdrawn by the investigator or the Principal Investigator if enrollment into the trial is inappropriate, the trial plan is violated, or for administrative and/or other safety reasons. Specific details regarding discontinuation or withdrawal are provided in Section 8.1.5.

A subject must be discontinued from the trial for any of the following reasons:

- The subject or legal representative (such as a parent or legal guardian) withdraws consent or decides to discontinue study therapy for any reason.

- Confirmed radiographic disease progression according to modified response criteria (see section 10.2).
- Unacceptable adverse experiences
- Intercurrent illness that prevents further administration of treatment
- Investigator's decision to withdraw the subject
- The subject has a confirmed positive serum pregnancy test
- Noncompliance with trial treatment or procedure requirements
- The subject is lost to follow-up
- Completed 24 months of treatment with MK-3475

Note: 24 months of study medication is calculated from the date of first dose. Subjects who stop MK-3475 after 24 months may be eligible for up to one year of additional study treatment if they progress after stopping study treatment provided they meet the requirements detailed in Section 8.1.6.1.2

- Administrative reasons

The End of Treatment and Follow-up visit procedures are listed in Section 7 (Protocol Flow Chart) and Section 8.1.6 (Visit Requirements). After the end of treatment, each subject will be followed for 30 days for adverse event monitoring. Subjects who discontinue for reasons other than progressive disease will have post-treatment follow-up for disease status until disease progression, initiating a non-study cancer treatment, withdrawing consent or becoming lost to follow-up. After documented disease progression each subject will be followed by telephone for overall survival until death, withdrawal of consent, or the end of the study, whichever occurs first.

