5. Patients should undergo CBC with differential count, a multiphasic profile consisting of serum electrolytes, BUN, serum creatinine, AST, ALT, serum bilirubin, alkaline phosphatase, and calcium with each treatment. . Baseline labs should be done within 2 weeks of the first dose of MK-3475. During the trial, laboratory tests can be done within 48 hours of the administration of MK-3475.
6. Patients should undergo Thyroid tests within 2 weeks of the first dose. These should be repeated at least every 4 cycles.
7. Patients should undergo appropriate scans, including brain scan, during screening, to document the status of the patient' cancer. The screening scans should be done within 3 weeks before the first dose of MK-3475. Patients should undergo appropriate scans to restage the patient after every 2 cycles for the first 6 cycles. For the first 6 cycles the re-staging scans should be performed within 1 week of the next cycle. After the first 6 cycles, the scans can be done as often as necessary by the treating physician but should be done at least every 4 cycles.
8. Archival tumor tissue will be retrieved to assess tumor PD-L1 status. Any tissue available should be submitted. Patient will be eligible even if tumor tissue cannot be submitted.
9. Patients will undergo blood collection for Circulating Tumor Cells (CTCs). This can be done on the first day of the first cycle prior to dosing MK-3475. This should also

be done on the first day of the second cycle and first day of the third cycle even if the drug is being held.

10. Patients who have completed 24 months on MK-3475 and stop therapy without progression can be retreated if patient has further progression. Patient will have to meet all original eligibility criteria and will be assessed and managed as a new patient starting on therapy. See section 8.1.6.
11. Every 12 weeks until the start of the next treatment for patient's cancer, disease progression, death, end of study.

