11.3 Analysis plan for primary and secondary endpoints

The primary endpoint, PFS, will be estimated with the standard Kaplan-Meier method, from which summary statistics of interest (median, 1-year rate, etc.) will be derived. Both point and 95% confidence interval estimates of PFS will be calculated. In this trial we will also assess PFS using modified criteria as well. It is well recognized that patients treated with immune therapy may have pseudo progression or can have delayed response. The modified PFS requires RECIST defined progression on 2 sequential scans at least 4 weeks apart for definition of progression. Overall survival is defined as the time from start of treatment to time of death. If the patient is lost to follow-up, survival will be censored on the last date the patient was known to be alive. All time-to-event endpoints will be estimated using standard Kaplan-Meier methods, from which the median and confidence interval will be calculated. Point and exact confidence interval estimates will be calculated for the toxicities and response rates. Cox model will be used to evaluate the association between time to event outcomes and covariates such as PD-L1 status and CTCs.

PD-L1 (yes/no) in tumor tissue and circulating tumor cells (CTCs) will be measured and their association will be studied with logistic regression. We will explore associations between PD-L1 and PFS, modified PFS, and OS using the Cox model. If biopsy samples are 15 patients or less, statistical analysis will be descriptive.

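### Modified PFS: the scan waiver in 10.2b omits the symptom-free patient who switches therapy at first RECIST progression, and 2.1 and 11.3 state different rules

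*Combined protocol and SAP*

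**What the plan says.** Section 3.2 lists modified PFS as the first secondary objective and points to 10.2 ("see section 10.2 for definition"). Section 6.5 also points there for the progression criterion that ends study participation.

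Section 10.2 asks for a confirming scan at least 4 weeks later. Item b drops it for patients with RECIST progression who are "symptomatic or have decline in performance status or develop unacceptable laboratory abnormalities and the treating physician and/or the patient decide to discontinue" or change therapy. Item a says that new lesions do not count as progression by themselves: their size is added to the tumor total, which must exceed a 20% threshold on two consecutive scans.

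Two other sections restate the rule:

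- Section 2.1 describes who needs two scans. After excepting patients with significant symptoms or a significant fall in performance status, it ends: "the patient/the treating physician feel the need to start next treatment, will require evidence of progression on 2 scans more than 4 weeks apart".
- Section 11.3 says: "The modified PFS requires RECIST defined progression on 2 sequential scans at least 4 weeks apart for definition of progression". It mentions no exception.

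Section 4.2.3 lets a patient come off therapy before confirmation because of symptoms, performance status, "or the patient wants to discontinue therapy for any reason". The rules for death and for patients without progression ("Patients who did not progress will be censored at the day of last tumor assessment") are written under the primary endpoint in 10.1 and repeated for it in 11.1.

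**The concern.** The definition leaves out a patient whom the protocol expects to exist. Sections 2.1 and 4.2.3 both foresee someone who feels well, has RECIST progression on a scan, and moves to another treatment. Section 10.2b gives that patient no waiver, and no confirming scan is planned after the switch. The analyst must then decide event status, possibly with outcomes already known in an open-label, single-arm trial.

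Section 2.1 promises RECIST PFS and modified PFS for all enrolled patients. The second measure exists because of pseudo-progression and delayed response, so a gap between the two curves will be read as a sign of those effects. If known progressors who switched are not counted, a gap appears even with no pseudo-progression. Modified PFS also enters the exploratory Cox models for PD-L1 in 11.3.

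**Working it through.** **1. The three statements side by side.** The test case is a patient with RECIST progression and no symptoms, performance status decline or laboratory abnormality, who stops to start another treatment.

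| Section | Second scan not needed if | Test case |
|---|---|---|
| 2.1 | symptoms, or performance status decline, or a felt need for next treatment | no second scan needed (natural reading) |
| 10.2b | symptoms, performance status decline or laboratory abnormality, with a decision to stop or change therapy | second scan needed |
| 11.3 | no exception stated | second scan needed |

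The or/and chain in 10.2b can be parsed two ways. In neither does a decision to switch suffice by itself. The interval also differs slightly: more than 4 weeks in 2.1, at least 4 weeks in 10.2 and 11.3.

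**2. Will a second scan exist?** Not by plan, once new therapy starts. Section 8.1.6.1.1 moves the patient to telephone contact every 12 weeks. Section 8.1.6.1 and flow chart note 11 ("Every 12 weeks until the start of the next treatment for patient's cancer, disease progression, death, end of study") end post-treatment imaging at that point.

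**3. The plan's own figure, as a check on the model.** Inputs from 11.2: exponential PFS, medians 2 and 3 months, one-sided alpha 0.05, 40 patients, 18 months accrual, 6 months minimum follow-up.

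- λ = ln 2/3 = 0.231 per month.
- Share with an event: 1 − (e^(−6λ) − e^(−24λ))/(18λ) = 1 − (0.2500 − 0.0039)/4.159 = 0.941.
- Expected events: 40 × 0.941 = 37.6; with 45 enrolled, 42.3.
- Power: Φ(√37.63 × ln 1.5 − 1.645) = Φ(0.842) = 0.800.

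This reproduces the stated 80%. It concerns RECIST PFS only and does not change. The plan states no figure for modified PFS.

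**4. Size of the effect on modified PFS.** Let f be the share of PFS events that are symptom-free switchers with no later scan. The documents give no value, so f is an assumption. Take exponential PFS with median m, no pseudo-progression, confirmed events dated at the first scan (10.2 does not say), and the f group censored at first progression, independently of prognosis. The event hazard falls from ln 2/m to (1 − f) × ln 2/m, so the median becomes m/(1 − f).

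| f | Patients of 45 (f × 42.3) | m = 3 months | m = 2 months |
|---|---|---|---|
| 5% | 2.1 | 3.16 | 2.11 |
| 10% | 4.2 | 3.33 | 2.22 |
| 20% | 8.5 | 3.75 | 2.50 |
| 30% | 12.7 | 4.29 | 2.86 |

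Simulated Kaplan-Meier medians for m = 3 (45 patients, 1,500 trials per setting) were 3.14, 3.38, 3.76 and 4.29, which agrees.

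**5. Against sampling error.** The approximate 95% interval for a 3-month median is 3 × exp(±1.96/√d). With d = 42.3 events it is 2.22 to 4.05 months; with d = 37.6 it is 2.18 to 4.13. Shifts for f of 5% to 20% lie inside it, but they all go the same way.

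**The case against.** The governing text can be identified. Sections 3.2 and 6.5 point to 10.2, section 2.1 is introductory narrative, and the sentence in 11.3 can be taken as shorthand. This stands. A reader might infer three competing definitions with none in charge, and the documents do not support that. It does not close the gap, because 10.2 itself leaves the switcher out.

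Four other strong readings also go too far.

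- *Section 2.1 scores the switcher as an event.* It never uses that term. It says, in awkward grammar, who needs two scans.
- *Modified PFS has no death or censoring rule.* Section 10.2 changes the progression criterion of the PFS just defined in 10.1, and the ordinary reading carries the other rules over. Saying so would help, but this is missing detail. The inherited rules do not clearly settle a patient with reported but unconfirmed progression.
- *Anyone who stops at first progression loses imaging.* Section 6.5 lists progression as a discontinuation reason only when confirmed by the modified criteria. A patient who stops earlier by choice can count as stopping for another reason and keep 12-weekly scans under 8.1.6.1. Other wording in 6.5 points the other way ("After documented disease progression each subject will be followed by telephone for overall survival until death"), as does note 11. The firm gap is the patient who starts new therapy.
- *An inactive drug could appear to reach 3 months.* Arithmetically 2/(1 − f) = 3 at f = 1/3. But the plan compares only RECIST PFS with 2 months, and nothing supports so large an f. Section 4.1 describes most of these patients as very symptomatic at diagnosis, and the default in 4.2.3 is to continue treatment until confirmation.

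Finally, if the switchers were instead counted as events at death, the medians in the table would not apply. The direction would be the same.

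**Conclusion.** The point holds as a gap in the definition of a secondary endpoint, made worse by differing wording in 2.1 and 11.3. As 10.2 and 11.3 are written, a symptom-free patient who switches therapy at first RECIST progression is not a progression event at that date, and no later scan is planned to make that patient one. Compared with counting the event at that date, this can only lengthen modified PFS, with or without pseudo-progression.

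The size depends on f, which is assumed and may be small. At f = 10%, about 4 of 45 patients, a 3.0-month median becomes 3.3 months if these patients are censored, under exponential times and independent censoring. That is within sampling error but one-directional. There is no test or decision rule on modified PFS, and RECIST PFS, the sample size and the power are untouched. It should be corrected before analysis; it does not threaten the trial's main conclusion.

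**What to change.** - **10.2b:** extend it so that a patient with RECIST progression who stops or changes therapy for any reason, with no later scan that confirms or refutes it, is a modified-PFS event on the date of that first progression. The same edit can state that confirmed events are dated at the first of the two scans.
- **New lesions:** keep 10.2a. Add the new-lesion measurement to the total and apply the extended rule only if the total then exceeds the 20% threshold. Otherwise censor at that scan and list the case. Scoring every new-lesion progression as an event would contradict 10.2a.
- **2.1 and 11.3:** replace the definitions with a reference to 10.2, with the interval given once as at least 4 weeks.
- **Death and censoring:** state for clarity that the 10.1 rules apply to modified PFS.
- **Reporting:** give the number of unconfirmed progressions by reason, with one sensitivity analysis that censors them.

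The cost is text edits to three sections, one count and one extra analysis. No scan, visit or patient is added. The downside is that true pseudo-progression among patients who stop is not credited; the sensitivity analysis shows how much this matters.
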